3.2. Primary Endpoint

The primary endpoint of the study is the Responder Rate, assessed 3 months post-procedure in the per protocol population of the Latera and Sham arms. Responder Rate is defined as the proportion of subjects with at least one (1) NOSE class improvement or at least 20% NOSE score reduction.

3.3. Secondary Endpoints

The following endpoints comprise the secondary endpoints and the time points that each will be assessed:

- Responder Rate at 7 days, 30 days, and 6, 12, 18 and 24 months;
- Frequency of procedure-related adverse events (non-serious and serious), assessed at the index procedure and through the 7-day, 30-day, 3-month, 6-month, 12-month, 18-month, and 24-month follow-up time points;
- Frequency of device-related adverse events (non-serious and serious), assessed at the index procedure and through the 7-day, 30-day, 3-month, 6-month, 12-month, 18-month and 24-month follow-up time points;
- NOSE score, change from baseline, to the 7-day, 30-day, 3-month, 6-month, 12-month, 18-month, and 24-month follow-up time points;
- Visual Analogue Scale (VAS), change from baseline, to the 7-day, 30-day, 3-month, 6-month, 12-month, 18-month, and 24-month follow-up time points;
- Endoscopic lateral wall insufficiency (LWI) score as assessed by independent reviewers, change from baseline to the 3-month and 6-month time points;
- Epworth Sleepiness Scale (ESS) score and Pittsburg Sleepiness Quality Index, change from baseline, to the 7-day, 30-day, 3-month, 6-month, 12-month, 18-month, and 24-month follow-up time points.

All secondary endpoints will be assessed for the Sham Control Arm at two additional visits. The Sham arm will have follow-up visits at 7 days, 30 days, and 3 months after the initial treatment/randomization, and 30 days, 3 months, 6, months, 12 months, 18 months, and 24 months in subjects that cross over.

4. STUDY POPULATION

Subjects will be recruited from sites' existing patient populations that are seeking treatment for nasal airway obstruction including nasal valve collapse. Anatomical considerations may impact the race distribution (e.g. some races may be less prone to lateral wall collapse), but the intention is to enroll all eligible subjects.

Spirox, Inc.
LATERA RCT

Study brochures containing information on study participation and the Latera Implant may be provided to the sites, as well as posters that may be displayed either as hard copies or electronically on computer monitors in the office. All recruiting materials must be approved by the appropriate IRB (central or local).

4.1. Patient Eligibility

The trial will include up to 150 subjects at up to 15 investigational sites, male and female, aged 18 and above who are appropriate candidates for nasal intervention with the Latera Implant.

Inclusion Criteria

Subjects must meet the following criteria to be included in the study:

- 1. Adults aged 18 and above;
- 2. Understands and provides written informed consent;
- 3. Stated willingness to comply with all study procedures, post-treatment care and availability for the duration of the study follow up of 2 years;
- 4. In good general health as evidenced by medical history;
- 5. NOSE score \geq 55;
- 6. Dynamic bi-lateral nasal wall insufficiency as confirmed by Positive Modified Cottle Maneuver;
- 7. Nasal and facial anatomy appropriate to receive the Latera Implant;
- 8. Documented failure of benefit after at least 4 weeks of conservative medical management, including, for example, antihistamines or nasal steroids, evidenced by lack of efficacy or tolerability.

Exclusion Criteria

Subjects meeting any one of the following criteria are ineligible for study participation:

- 1. Unable to tolerate or not a candidate for procedures performed under local anesthesia;
- 2. Pathology other than lateral wall insufficiency (e.g. septal deviation, turbinate or adenoid hypertrophy, polyps, sinusitis, rhinitis) is the primary contributor to airway obstruction;
- 3. Requires or is anticipated to require any other concurrent nasal procedures (e.g. Functional Endoscopic Sinus Surgery (FESS), rhinoplasty, sinuplasty, septoplasty, or turbinate reduction) outside of the index procedure within 12 months after the index procedure;
- 4. FESS, sinuplasty, septoplasty, inferior turbinate reduction, or rhinoplasty within the past 6 months;
- 5. Any other rhinoplasty procedures are planned or planned usage of external dilators within 24 months after the index procedure;
- 6. Permanent nasal implant of any type (e.g. autologous, homologous, or synthetic graft) or dilator;
- 7. Presence of concomitant inflammatory or infectious conditions or unhealed wounds in the treatment area (e.g., vestibulitis, vasculitis, active acne),

- 8. Currently use of chronic systemic steroids or recreational intra-nasal drugs;
- 9. Currently has cancerous or pre-cancerous nasal lesions, has had radiation in the treatment area, or is currently receiving chemotherapy;
- 10. History of a significant healing disorders including hypertrophic scarring, or keloid formation;
- 11. Poorly controlled diabetes mellitus;
- 12. Known or suspected allergy to PLA or other absorbable implant materials in the Latera Implant;
- 13. Severe obstructive sleep apnea (OSA) and cannot or is unwilling to refrain from continuous positive airway pressure (CPAP) for up to 2 weeks post-procedure based on expected healing needs and mask type, in agreement with the treating physician;
- 14. Female subjects, of child bearing potential, known or suspected to be pregnant or are lactating;
- 15. Any other presenting condition that, in the medical opinion of the investigator, would disqualify the subject from the study.

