2.5. Device Description

The absorbable nasal Implant is comprised of a 70:30 blend of poly(L-lactide) and poly(D-lactide). The Implant is predominantly cylindrical in shape with a diameter of 1 mm and an overall length of 24 mm with a forked distal end for anchoring and features on the proximal end for increased flexibility. The copolymer is absorbed by the body over a period of approximately 18 months.¹⁸ The Latera Implant is provided in a plastic tray with a sliding lid. The Implant and plastic tray are depicted in **Figure 2**, below.

Figure 2: LATERA Absorbable Nasal Implant and Packaging

The Delivery Device is a single use device composed of an inner shaft, an outer handle with a push rod, a deploy button, an open button and a 16-gauge delivery cannula with a protective cover. The inner shaft includes an implant loading port which enables the loading of the Implant. The inner shaft transitions between the loading position and the cannula to collapse the implant forks within the cannula inner lumen and prepare the Implant for deployment. The outer handle includes deploy and open buttons that lock and release the handle from these respective positions. The outer handle also includes a push rod that shuttles the implant from the implant loading port to a ready position for deployment. The Implant Positioning Guide is packaged with the Delivery Device and is provided as an aid to the physician for planning the procedure and identifying the target Implant location. The Delivery Device and the Implant Positioning Guide are shown in **Figure 3** below.

Figure 3. Delivery device and implant positioning guide.

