5. STUDY PROCEDURES AND FOLLOW-UP EVALUATIONS

5.1. Screening/Baseline Assessment

All patients seeking treatment for nasal obstruction will be screened for eligibility according to the inclusion/exclusion criteria. A member of the site's research team will review the patient's medical history for eligibility and potential inclusion into the study.

The Investigator or their designee will inform the patient about the purpose of the study and will explain the potential benefits and risks of both study arms, the Latera Implant and/or the Sham Control arm. Potential subjects will be counseled as to the nature of their condition. All subjects will have ample time to ask questions.

Patients indicating that they would like to proceed with study participation, and who are willing to comply with the requirements of the study protocol, will be asked to sign an Informed Consent Form (ICF) that has been approved by the governing IRB. Failure to provide written informed consent makes the patient ineligible for the study.

Female patients of childbearing potential will undergo a pregnancy test to verify eligibility. Women of childbearing potential are defined as any female who has experienced menarche and who is NOT permanently sterile or postmenopausal. Postmenopausal is defined as twelve (12) consecutive months with no menses without an alternative medical cause.

Patients will be considered enrolled as study subjects upon signing the ICF and meeting all study eligibility criteria. Once the subject has been enrolled into the study a baseline assessment will be completed.

The following baseline data will be collected at the Screening/Baseline visit prior to the procedure. All data must be recorded in the study specific EDC for Latera RCT within 5 business days.

• Nasal Obstruction Symptom Evaluation (NOSE) scale

- Epworth Sleepiness Scale (ESS)
- Pittsburg Sleep Quality Index (PSQI)
- NAO Breathing Assessment
- Demographic information
- Abbreviated Medical History
- Nasal medical history including risk factors
- Nasal Exam including assessment of the septum and turbinates
- Modified Cottle Maneuver
- Lateral Wall Motion Video
- LateraTM Implants may involve unknown risks to a pregnant woman, an embryo, fetus (unborn baby) or nursing infant. Any female that is pregnant, planning to become pregnant or is breastfeeding a child, cannot participate in this study. All women of childbearing potential will have a pregnancy test done prior to treatment.

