Adverse events that occurred after the ICF was signed, should be entered in the EDC within 1 business day of completion of the visit.

Treatment must occur within 30 days of the date of consent. If the subject is not treated within 30 days, they will be exited from the study with no further follow-up.

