Nasal Medical History & Exam	Х										
Eligibility	Х										
Lateral Wall Motion Video	Х				Х			Х			
Turbinate Hypertrophy and Septum Assessment	Х										
Nasal Obstruction Evaluation (NOSE)	Х		Х	Х	Х	Х		Х	X	X	Х
Sleep Assessments (ESS & PSQI)	Х		Х	Х	Х	Х		Х	X	X	Х
Photograph – Planning Images	Х										
Pregnancy Test	Х					X					
Nasal Breathing Assessment (VAS)	Х		Х	Х	Х	X		Х	Х	Х	X
Randomization		Х									
Procedure Logistics		Х					Х				
Relevant Medications	Х		Х	Х	Х			Х	Х	Х	Х
Adverse Events	Х	X	Х	Х	Х		Х	Х	X	X	X

Note: *For Sham Control Subjects that cross-over after 90 day assessment for primary endpoint and meet stu eligibility for a Latera Implant, per the protocol, will have repeat 30 and 90 day visits, in addition to all the otl visits.

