11. ETHICS

11.1. Informed Consent

Written informed consent must be obtained for each subject before any study-specific procedures or assessments are done and, specifically, prior to the subject being treated with the Latera implant. The methods used in the Latera RCT will include an electronic informed consent (eIC) and traditional paper. The Investigator or designee, trained on the protocol, will explain the nature, scope, anticipated benefits, and potential risks involved in the study. Written informed consent will be obtained after the aims, methods, anticipated benefits, and potential risks are explained.

All subjects may receive a stipend for their time and to cover travel costs for participation in the Latera RCT. The stipend and schedule must be approved by the investigational site's recognized IRB (central

IRB or local). The plans for the study is as follows: After completion the following study visits, subjects will receive a \$50.00 prepaid debit card at end of the following visits: Baseline visit, Treatment, one (1) week, one (1), three (3), and six (6) month; and they will receive a \$100.00 prepaid debit card for twelve (12), eighteen (18) and twenty-four (24) month study visits. The total compensation to each subject will be \$600.00 for completion of all of the study visits for the Latera Implant group of the study or it will be \$750.00 for completion of all the study visits for the Sham treatment group of the study.

If required by institutional policy, informed consent will be obtained prior to review of Baseline and Screening data. A Screening Consent Form may also be available to secure permission from the subject for reviewing prospective subject information (if requested/required by site or IRB policy) prior to the subject agreeing to participate in the trial and signing the study-specific Informed Consent Form.

Consenting addendums will be used to confirm continuing patient consent in the cases of re-implanting procedures and the cross-over implant procedures.

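### Protocol 5.1 bars women who are planning a pregnancy, but exclusion 14, the numbered criterion for this topic, does not mention them

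*Protocol*

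**What the plan says.** Exclusion 14 in Protocol 4.1 covers "Female subjects, of child bearing potential, known or suspected to be pregnant or are lactating". The synopsis and the exclusion list under SAP 2.3.1 repeat it.

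Protocol 5.1, on screening and baseline, first opens screening to patients seeking treatment and ties it to the inclusion and exclusion criteria. It then lists the baseline data to be collected: scales, histories, examination, video. The last bullet of that list is not a data item. It states that the implant may carry risks not yet known for a pregnant woman, embryo, fetus or nursing infant, and adds: "Any female that is pregnant, planning to become pregnant or is breastfeeding a child, cannot participate in this study". No time horizon is attached to planning.

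Protocol 5.3 lets a sham subject cross over after the 3-month evaluation if she still meets the inclusion and exclusion criteria. The synopsis and Protocol 6.3 also make cross-over depend on eligibility.

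**The concern.** The protocol states a fetal-risk reason and a categorical bar, then leaves part of that bar out of the list by which it defines eligibility. The missing part is the one that a pregnancy test cannot detect: an intention to conceive is found only by asking, and the numbered list gives a site no prompt to ask.

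Three things are at stake. A woman the protocol means to keep out could be enrolled by a site that followed the numbered list faithfully. The question arises again at cross-over, when a sham subject is about to receive an implant and her plans may have changed since baseline. And Protocol 7.3 makes inclusion of a subject outside eligibility a deviation, so a site and a monitor could disagree on whether enrolling this woman is one.

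**Working it through.** No figure in the plan bears on this point, so the check is a comparison of texts.

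**Step 1: set the two rules side by side.**

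| Status of the woman | Exclusion 14 (synopsis, Protocol 4.1, SAP 2.3.1) | Bullet in Protocol 5.1 |
|---|---|---|
| Pregnant | excluded | barred |
| Suspected pregnant | excluded | not named |
| Lactating or breastfeeding | excluded | barred |
| Planning a pregnancy | not named | barred |

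The last row is the mismatch.

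**Step 2: look for another numbered criterion that closes it.** The only candidate is exclusion 15, which lets the investigator exclude for another presenting condition. It is discretionary and does not name planned pregnancy, whereas the 5.1 bar is mandatory. None of the inclusion criteria mentions it.

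**Step 3: establish which text governs the decision.** Protocol 5.1 and 6.2 define enrolment as a signed consent form plus meeting all eligibility criteria. The section headed Patient Eligibility is 4.1. Cross-over under 5.3 refers to the same criteria. Both decisions therefore point to the list that lacks the bar.

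**Step 4: apply the rules to one patient.** Take a woman who is not pregnant, not suspected to be, not lactating, and who says she intends to conceive during follow-up. Under exclusions 1 to 15, if nothing else applies and the investigator does not invoke exclusion 15, she passes. Under 5.1 she cannot take part. Nothing in either document says how the two are to be combined.

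**Step 5: check the statistical consequence.** The ITT definition in Protocol 6.2 disregards adherence to entry criteria. The per-protocol definition turns on treatment, a NOSE assessment within the 3-month window and, under 6.3, absence of early unblinding. Neither removes a subject for an eligibility deviation, so the mismatch does not alter the primary analysis set, the 124 evaluable subjects or the error rates.

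**The case against.** The strongest reply is that 5.1 is protocol text like any other and sits in the section that governs screening. Exclusion 14 is silent on planned pregnancy and does not permit it, so the two can be read cumulatively, and investigators undertake to follow the whole protocol. This stands in part. It rules out saying that the rules give opposite answers or that the protocol allows these women to be treated. It does not remove the omission, because the section that defines eligibility is the one without the bar.

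A second reply is that the working tools may already carry the bar. The consent form and case report forms are attachments whose content is not available here. That is fair: actual differences between sites cannot be shown, only that the numbered list allows them.

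A reader might also infer a conflict over test timing. Under Protocol 11.1, "Written informed consent must be obtained for each subject before any study-specific procedures or assessments are done", so the earliest study test is on the day of consent, day 0. Protocol 5.1 adds: "Treatment must occur within 30 days of the date of consent". The test could then be up to 30 − 0 = 30 days old at the index procedure. But the documents do not contradict themselves here. Protocol 5.1 says "Female patients of childbearing potential will undergo a pregnancy test to verify eligibility" and "All women of childbearing potential will have a pregnancy test done prior to treatment"; a screening test satisfies both sentences. In Table 2 the "Pregnancy Test" row is marked at Screening/Baseline and again at Cross-Over Screening, which agrees with that text. A maximum test age would be a new clinical rule.

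Nor should the absorption time be read as the size of the problem. Protocol 2.5 states: "The copolymer is absorbed by the body over a period of approximately 18 months". The documents set no contraception requirement, so conception during that period could also occur under a fully reconciled eligibility rule.

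**Conclusion.** The point holds as an inconsistency by omission. Protocol 5.1 bars women planning a pregnancy on a stated fetal-risk ground, and exclusion 14 leaves them out in all three places where it appears. A site screening from the numbered list could enrol or cross over a woman whom 5.1 bars.

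Its size in patients is unknown, because neither document gives the number of women of childbearing potential or of those planning a pregnancy. The ceiling is only that it could arise at any of up to 15 sites, at index screening and again at cross-over. It has no effect on power or type I error. It is worth correcting because it concerns a safeguard the protocol itself sets out.

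The conclusion assumes that sites take eligibility from the numbered criteria, as 5.1 and 5.3 direct, and that no unseen form already states the bar.

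**What to change.** Reconcile Protocol 5.1 with exclusion 14 so that one rule on planned pregnancy stands in the numbered list used at index and cross-over screening, with 5.1 worded to match. The sponsor's clinicians should choose the rule, including what counts as planning; this review does not say which is right. Carry the result to the synopsis and to SAP 2.3.1. The SAP copy is the least urgent, since sites do not enrol from it, and SAP version 1.0 (12 February 2018) predates Protocol version 3.0 (23 March 2018). The eligibility and consent forms should be checked against the chosen rule at the same time.

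No change to the pregnancy-test row of Table 2 is needed on this ground. The cost is a wording amendment with IRB review and, depending on the rule chosen, possibly a few candidates who become ineligible.

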4.2. Patient Screening and Informed Consent

The investigator or designee, who is trained on the study protocol, will review and explain the study protocol and information, including the potential risks and benefits of participation. Time will be made available for the patient to read through the materials and ask questions. A study and protocol-specific Informed Consent Form (ICF), approved by a central or appropriate local Institutional Review Board (IRB) will be obtained from each subject prior to enrollment in the study. An electronic consent (eConsent) will be available on a web-based module of the study's electronic data capture (EDC) system. Alternatively, Investigators may utilize a standard written consent form. In either case, subjects will be provided with a hardcopy of the executed ICF. All subjects will be instructed that they are free to decline entry into the study or to withdraw from the study at any time without prejudice to future treatment. After completion of the consenting process and eligibility has been confirmed, subjects will be considered consented and enrolled for the study duration of up to 27 months of follow-up.

4.3. Subject Disposition and Flow Chart

The graphic below illustrates the flow of subjects in the study and potential points of study exit relative to analysis plan (**Figure 4**, page 23, below). Subjects are enrolled at the time of consent, and the ITT population is comprised of all consented subjects. Subjects are randomized after the anesthetic is administered. Subjects in the active treatment group receive the Latera implant, while those in the Sham Control group will undergo insertion of the cannula into the nasal lateral wall, but the Latera will not be implanted. The mITT population includes all subjects who were randomized, irrespective of whether they received the study device. The PP population includes those subjects who received the study device or the Sham Control and who are followed through 3 months.

Figure 4. Flow of subjects in the trial and definitions of the ITT, mITT and PP populations.

4.4. Withdrawals and Loss to Follow-up

Participation is completely voluntary and each subject is free to withdraw from the study at any time. An investigator also has the right to withdraw the subject from the study in the event of reasons concerning the health or well-being of the subject, or in the case of lack of cooperation. Should a subject decide to withdraw for any reason, or should the investigator decide to withdraw the subject, all efforts will be made to complete and report the observations up to the time of withdrawal as thoroughly as possible. A complete final evaluation at the time of the subject's withdrawal must be made and an explanation given of why the subject is withdrawing or being withdrawn from the study.

The reason for and date of withdrawal must be recorded on the subject's Study Exit Case Report Form (CRF). If the reason for the withdrawal is a device-related or procedure related AE, the event must be reported to the Sponsor and recorded in the AE CRF.

Withdrawal can occur at several time-points that would impact the follow up schedule for a study subject. If withdrawal occurs any time before the treatment procedure, anesthesia and randomization, the subject will be exited with no follow up assessment requirements. If withdrawal occurs after anesthesia,

regardless of whether randomization is complete, subjects will be followed through the 3 months follow up assessment and then exited from the study.

All efforts will be made to retain subjects in order to collect data at all the follow-up visits (7 days, 30 days, 3 months, 6 months, 12 months, 18 months, 24 months). Due diligence in reaching the subject must include:

- Two documented telephone contact attempts, emails, or regular postal mail letters, and
- A certified letter

After the above attempts are made, if no response is obtained, the Study Exit CRF page will need to be completed and communication attempts will need to be documented.

